# 1. Background

Montana’s high rates of poor mental health combined with low rates of access to care [1] indicate a pressing urgency for alternative methods to meet the mental health needs of Montanans. Mental health service deficits in rural and frontier Montana communities, compared to more urban areas are even more substantial [2] where higher poverty, lower educational attainment, and lower employment rates occur [3]. Montana ranks last among all states in population density with 55 of 56 counties defined as rural or frontier [4].

Computer-administered CBT (cCBT) programs have generally shown similar efficacy as clinician-administered CBT [5] with positive impacts in rural communities outside the U.S. [6]. *Thrive* is an interactive version of cCBT with a heavy emphasis on video rather than text content that appears to improve participant engagement, a shortcoming seen in prior cCBT programs [7]. *Thrive* users proceed at their own pace and receive personalized treatment sequences based on assessment responses by each patient. *Thrive* provides safeguards and guidance if the program is not working effectively.

*Thrive*’s developmental history reflects changes in accessible technology. Across all developmental versions, it has been shown to be efficacious in reducing depressive symptoms. First developed and studied as a desk top computer terminal administered program in a RCT compared with clinician CBT and wait-list control (WLC), it’s early promise was reflected in effect sizes of 1.37 and 1.26 for computer treated and therapist treated groups, respectively, compared with WLC [8]. A substantially modified version called COPE was administered by telephone via interactive voice response [9]. COPE was subsequently converted for administration on the Internet and improved by reducing text and implementing use of videos, making the program more engaging and effective for individuals with lower literacy. It has since been designed to operate on smartphone and tablet devices in addition to computers. To provide a gold-standard test of efficacy of cCBT in rural U.S. communities, RCTs are needed. Given the high stigmatization of mental illness in remote rural communities [10], cCBT programs such as *Thrive* offer an accessible and confidential way to help people experiencing depressive symptoms, syndromes, and disorders in rural communities. Our project addresses this need.

*Preliminary evidence on Thrive.* Among commercially insured patients, *Thrive* resulted in an average reduction of 39% in depression severity as measured by the Patient Health Questionnaire-9 (PHQ-9) [11], from pre- to post-assessment (see Table). These uncontrolled trials indicate improvements in depression symptoms across all levels of baseline depression severity with marked improvements among those with moderate to severe depression.

## Thrive Outcomes Among Commercially Insured Patients (N = 297)

	Baseline PHQ-9 Score Range*					Total
	0-4	5-9	10-14	15-19	20-27	
	None	Mild	Moderate	Mod Severe	Severe	
Number of Enrollees with	88	104	68	29	8	297

PHQ-9 Score of $\geq 2$						
Mean Baseline Score	2.4	7.0	11.5	16.8	21.9	8.0
Mean Endpoint Score	2.0	4.6	6.5	8.7	12.0	4.9
Change in Mean Score	-0.4	-2.4	-5.1	-8.1	-9.9	-3.2
% Improvement in Score	17%	34%	44%	48%	45%	39%
Effect Size	0.22	1.12	1.82	2.30	2.35	0.67

\*PHQ-9 score range based on 9 items with a 4-point response scale of 0 to 3

## 2. Research Objectives

This is a fully randomized trial of cCBT care for depression versus care as usual. The quantitative evaluation will be completed to achieve the following aims:

1. To determine the relative effectiveness of the *Thrive* program to decrease depressive symptomatology and improve overall quality of life compared to usual care.
2. To determine the long-term effectiveness of the *Thrive* program to decrease depressive symptomatology and improve overall quality of life

## 3. Methods

### 3.1 Design

This study uses a randomized wait-list controlled design, whereby participants will be assigned either to receive the *Thrive* program immediately upon enrollment for 8 weeks or wait 8 weeks following enrollment to receive the *Thrive* program. Subjects will be followed for a total of one year following delivery of *Thrive* to provide an exploratory evaluation of its long-term impact. During the RCT period, those randomized to the control group will receive basic information about depression from the National Institute of Mental Health [21], and will subsequently be provided access to the *Thrive* program at the end of the initial eight-weeks of the study trial.

### 3.2 Inclusion/Exclusion Criteria

**3.2.1 Inclusion Criteria:** Participants must be aged 18 year or older; have residency in Montana, have regular access to broadband internet, and have a score of 5 or greater on the Patient Health Questionnaire-9.

**3.2.2 Exclusion Criteria:** We will exclude persons aged 17 year or younger, non-residents of Montana, those who do not have access to broadband internet, and have a score of 4 or lower on the Patient Health Questionnaire-9.

### 3.3 Recruitment and Randomization

Community members will be recruited for participation in the RCT via channels identified from key informant interviews and focus group sessions. Example channels include

state Extension agents, Facebook, identified organization email listservs, and community flyers. A study enrollment and assessment portal will randomly assign each participant to either the intervention or wait-list control (WLC) groups.

### 3.4 Measures and data collection

**Primary Outcome Measure:** Patient Health Questionnaire nine-item scale (PHQ-9) [11], is a valid assessments of depression severity

**Secondary Outcome Measures:** Generalized Anxiety Disorder seven-item scale (GAD-7) [12]; Connor-Davidson Resilience ten-item Scale (CDRS-10) [13]; and, the Work and Social Adjustment Scale (WSAS) [14].

Data are collected by self-report online and will be uploaded and de-identified through the *Thrive* database and made accessible to the PI for monitoring and analysis. Participants randomized to the intervention group are assessed at baseline, 4 and 8 weeks, and 6 and 12 months from enrollment. Participants randomized to the waitlist control group are assessed at baseline, 4, 8, 12, and 16 weeks, and 8 and 14 months from enrollment.

**3.5 Statistical Analysis Plan:** Analyses will use an intent-to-treat approach to examine difference in mean scores between intervention and control groups. Depressive symptomatology (PHQ-9 scores) from baseline and weeks 4 and 8 will be the primary continuous outcome measure. Anxiety, Resilience, and Functional Impairment scores from baseline and weeks 4 and 8 will be secondary continuous outcome measures. For the primary and secondary outcomes, the change over time in each outcome will be compared between the intervention and WLC groups using a linear mixed model analysis of repeated measures. A separate mixed model will be conducted on each outcome measure. Each mixed model will contain fixed effects terms for treatment (intervention vs. WLC), time, treatment  $\times$  time interaction, and respective baseline measure (prior to the intervention) as a covariate. Other relevant covariates will also be considered for inclusion in the mixed model. The correlation of any naturally-occurring paired participants (e.g., parent/child, siblings, husband/wife, and partners) will be accounted for in the mixed model analysis. Least squares (LS) means (adjusted treatment means) will be estimated as part of the mixed model so as to interpret the omnibus treatment effect (LS mean difference between treatments). Statistical analyses will be performed using SAS software, version 9.4 (SAS Institute, Inc., Cary, NC). The PROC MIXED procedures (mixed model approach in SAS) will make use of all available data from all participants from the efficacy analysis set, and provide a robust mechanism for handling data that are assumed missing at random [15-17]. The level of significance for all tests will be set at  $\alpha = .05$  (two-tailed). Statistical expertise will be built into the budget for Years 1 and 2.

To evaluate the long-term effects of *Thrive*, in an exploratory analysis, a completely within-subjects linear mixed model analysis of repeated measures will be used to examine the change in each of the primary and secondary outcomes over the 12 months following delivery of *Thrive* by combining data from both treatment groups (intervention+WLC). In the case of the group randomized to *Thrive*, data will include assessments at baseline, 4 and 8 weeks, and 6 and 12 months. For the WLC group, baseline for this combined-group analysis will be 8

weeks after randomization (i.e., immediately prior to starting *Thrive*) and then 4 and 8 weeks, and 6 and 12 months after starting *Thrive*.

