### **3.6 Sample Size Estimation and Power Analysis for the Primary Outcome of the Study:**

Effect sizes from the preliminary analysis of the 4 uncontrolled studies of *Thrive* as it relates to the primary continuous outcome (depressive symptomatology, as assessed by the PHQ-9) were consistently very large ( $d > 1.0$ ). Using a conservative estimate of effect size ( $d \sim 0.30$ ), an a priori sample size estimation and power analysis was performed for the repeated measures design/analysis in the proposed controlled study. The results suggest that a sample size of 117 per group ( $N = 234$ ) achieves 80% power to detect a conservative effect size of 0.30 (Cohen's  $d$ --standardized group mean difference) in a 2 (between-subjects) group design with 3 (within-subjects) repeated measurements having a compound symmetry covariance structure when the assumed within-subject correlation is 0.50, and the alpha level is 0.05 (two-tailed), with a normal distribution for the test statistic. We anticipate some dropouts [ $\sim 49\%$  within the first 4 weeks (the period designating an evaluable subject) after enrollment, based on treatment discontinuation results from *Thrive*]. Thus, 459 participants will be enrolled to allow for this expected rate of attrition with the intent of capturing a range of evaluable data for 234 participants. The Power Analysis and Sample Size (PASS) 2015 software, version 14.02, was used to carry out the sample size and power analysis [18].

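### Section 3.5 lists baseline as both response and covariate, so the omnibus effect is two thirds of the week 4/8 effect; dropping baseline as a response leaves a model that 3.6 does not describe

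*Combined protocol and SAP*

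**What the plan says.** Four statements bear on this point.

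- **Response (3.5).** "Depressive symptomatology (PHQ-9 scores) from baseline and weeks 4 and 8 will be the primary continuous outcome measure". The secondary outcomes follow the same pattern: "Anxiety, Resilience, and Functional Impairment scores from baseline and weeks 4 and 8 will be secondary continuous outcome measures".
- **Model terms (3.5).** Treatment, time, their interaction, and the "respective baseline measure (prior to the intervention) as a covariate".
- **Effect to be read off (3.5).** The aim is that "the change over time in each outcome will be compared between the intervention and WLC groups", and LS means are estimated to "interpret the omnibus treatment effect (LS mean difference between treatments". No week, or average of weeks, is attached to that difference.
- **Sample size (3.6).** 117 per group gives 80% power for d = 0.30 in a two-group design with "3 (within-subjects) repeated measurements having a compound symmetry covariance structure", correlation 0.50, two-sided alpha 0.05. No baseline covariate is mentioned.

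Section 3.4 gives the intervention-arm schedule: "Participants randomized to the intervention group are assessed at baseline, 4 and 8 weeks, and 6 and 12 months from enrollment". The wait-list arm is also assessed at baseline, 4 and 8 weeks before it receives *Thrive*. The 8-week randomized period therefore holds exactly three assessments, and one of them is baseline.

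**The concern.** Section 3.5 can be implemented in two ways.

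1. **Literal.** Baseline, week 4 and week 8 are all responses, and baseline is also a covariate. The omnibus LS-mean difference then averages in a time point at which no treatment effect can exist.
2. **Weeks 4 and 8 only.** These are the responses and baseline is a covariate. This is a standard model, but it has two measurements where 3.6 counts three.

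At stake is the size of the reported primary effect. Two analysts who both follow 3.5 could report 0.20 or 0.30 SD from the same trial, and the same ambiguity affects GAD-7, CDRS-10 and WSAS. On the literal reading there is also a question about the validity of some tests.

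**Working it through.** **Inputs.** From 3.6: d = 0.30, correlation ρ = 0.50, compound symmetry, alpha 0.05 two-sided, 117 per group. SD is set to 1. Formula: n per group = 2V(1.96 + 0.8416)²/0.30², where V is the variance of the analysed quantity.

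**Step 1: the plan's own figure.** For the mean of three unadjusted measurements, V = (1 + 2ρ)/3 = 0.667, so n = 116.3, rounded up to 117. This reproduces 3.6. It requires d = 0.30 at all three measurements, including baseline.

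**Step 2: literal model, size of the estimate.** The omnibus difference with equal weights is (d0 + d4 + d8)/3. Randomization gives an expected d0 of 0. With d4 = d8 = 0.30 the result is 0.60/3 = 0.20, which is two thirds of 0.30. With complete data and compound symmetry the ratio is exact in each trial: a participant's mean is baseline/3 plus two thirds of the week 4/8 average, and the covariate absorbs the first part.

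**Step 3: literal model, power with complete data.** The baseline-adjusted week 4/8 average has V = (1 + ρ)/2 − ρ² = 0.50, so SE = √(2 × 0.50/117) = 0.0925. The literal omnibus SE is two thirds of that, 0.0616. Since 0.20/0.0616 = 0.30/0.0925 = 3.245, the test is the same, with power Φ(3.245 − 1.96) = 90%.

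**Step 4: literal model, contrasts at week 8 or over weeks 4/8.** With complete data the fitted baseline slope is (1 + 2ρ)/3 = 2/3.

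- Residual variance is (1 − 2/3)² = 0.111 at baseline and 1 + 4/9 − 2(2/3)(0.5) = 0.778 at week 4 and at week 8.
- A common-variance fit uses their average, (0.111 + 0.778 + 0.778)/3 = 0.556. The week-8 SE is therefore too small by a factor √(0.556/0.778) = 0.845, and null rejection is 2[1 − Φ(1.96 × 0.845)] = 9.8%.
- For the week 4/8 average, the true variance is 0.75 + 4/9 − 2(2/3)(0.5) = 0.528. The fit splits 0.556 into a between-participant part of 0.056 and a within-participant part of 0.50, so it uses 0.056 + 0.50/2 = 0.306. The factor is √(0.306/0.528) = 0.761, and null rejection is 13.6%.

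Simulation under compound symmetry gave 9.4% to 10.0% for week 8 and 13.2% to 13.5% for the average.

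**Step 5: literal model, omnibus test with missing data.** Simulated null rejection (compound-symmetry fit, ρ = 0.50, dropout completely at random; the missing shares are assumptions):

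| Post-baseline data | Omnibus type I error |
|---|---|
| Complete | 5% |
| Week 8 only missing, 20% to 40% in both arms | about 6% to 7% |
| Baseline only, participants kept, 20% in both arms | about 7% |
| Baseline only, participants kept, 49% in both arms | up to about 14% |

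The model with weeks 4 and 8 as the only responses rejected in 4.5% to 5.6% of null trials in the baseline-only and complete-data scenarios.

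**Step 6: weeks 4 and 8 only, set against 3.6.**

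| Contrast, baseline-adjusted | V | n per group for 80% | Power at 117 (ρ = 0.50) | Power at 117 (ρ = 0.3 to 0.7) |
|---|---|---|---|---|
| Week 4/8 average | (1 + ρ)/2 − ρ² = 0.50 | 88 | 90% | 87% to 97% |
| Week 8 alone | 1 − ρ² = 0.75 | 131 | 75% | 67% to 89% |

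Neither row is the calculation in 3.6.

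**The case against.** The strongest reply is that the literal model is not clearly intended. The outcome sentence may only list the data used, and the sentence that specifies the model gives baseline one role, as a covariate. An experienced analyst would probably fit weeks 4 and 8. One who tried the literal model with a separate variance at each time would probably notice a fault, because a covariate slope of 1 makes every baseline residual zero and the likelihood has no maximum. This has weight, and it is why the dilution is stated as conditional. It does not close the matter: 3.5 never removes baseline from the response, and the three measurements in 3.6 fit the randomized period only if baseline is one of them.

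Four stronger readings are tempting, and the documents do not support them.

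- *The trial is underpowered.* A reader might set the diluted 0.20 against the variance in 3.6 and get 47% power, or take two unadjusted measurements and get 75%. Both leave out the covariate that 3.5 requires. With it, the week 4/8 average has about 90% power.
- *The omnibus test is invalid in general.* With complete data it holds at 5%. The 14% needs the literal reading, a common-variance fit, and 49% with baseline only in both arms and kept. Section 3.6 takes its 49% from discontinuation of *Thrive*, which the wait-list arm does not have in the first 8 weeks. It also treats the first 4 weeks as defining who is evaluable, which lends some support to excluding baseline-only participants. Against that stand the intent-to-treat wording and the statement that the procedure "will make use of all available data from all participants from the efficacy analysis set", a set that 3.5 does not define.
- *Excluding baseline-only participants cures the literal model.* It does not: missing week 8 alone takes the omnibus error to about 6% to 7%.
- *Poor interval coverage is a further harm.* The literal interval contains 0.30 in only about 63% of complete-data trials, but that restates the dilution, since the interval is centred on 0.20.

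**Conclusion.** The concern holds in conditional form and should be fixed. On the literal reading the omnibus estimate and its confidence interval shrink by one third for PHQ-9 and for the three secondary outcomes. This rests on randomization and equal LS-mean weights, and does not depend on the size of the effect. The error is toward a smaller effect and costs no power when data are complete. The excess type I error, for the week-8 and week 4/8 contrasts and for the omnibus test with missing data, rests in addition on a common-variance structure, ρ = 0.50 and, for the omnibus test, the assumed dropout. On the other reading the estimate is sound and the planned size is more than enough for the week 4/8 average, but 3.6 justifies that size with an effect at baseline, where none can exist. No reading makes 3.5 and 3.6 agree on a model that estimates the treatment effect without dilution.

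**What to change.** In 3.5, state that the responses are weeks 4 and 8 only, with baseline as covariate and terms for treatment, time and treatment × time. Name the LS-mean difference averaged over weeks 4 and 8 as the primary contrast, and report week 8 as supportive. Apply the same model to GAD-7, CDRS-10 and WSAS. Under this model a participant with baseline only contributes no response, so the inflation in step 5 does not arise by that route.

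Restate 3.6 for that model and contrast: at ρ = 0.50, 88 per group gives 80% power and the planned 117 gives about 90% (87% to 97% for ρ from 0.3 to 0.7). If the sponsor prefers week 8 as primary, 3.6 must state about 75% power at 117 per group, which is below its 80% target.

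The cost is SAP wording and a restated 3.6, with no new visits and no added enrollment.

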### **3.6 Sample Size Estimation and Power Analysis for the Primary Outcome of the Study:**

Effect sizes from the preliminary analysis of the 4 uncontrolled studies of *Thrive* as it relates to the primary continuous outcome (depressive symptomatology, as assessed by the PHQ-9) were consistently very large ( $d > 1.0$ ). Using a conservative estimate of effect size ( $d \sim 0.30$ ), an a priori sample size estimation and power analysis was performed for the repeated measures design/analysis in the proposed controlled study. The results suggest that a sample size of 117 per group ( $N = 234$ ) achieves 80% power to detect a conservative effect size of 0.30 (Cohen's  $d$ --standardized group mean difference) in a 2 (between-subjects) group design with 3 (within-subjects) repeated measurements having a compound symmetry covariance structure when the assumed within-subject correlation is 0.50, and the alpha level is 0.05 (two-tailed), with a normal distribution for the test statistic. We anticipate some dropouts [ $\sim 49\%$  within the first 4 weeks (the period designating an evaluable subject) after enrollment, based on treatment discontinuation results from *Thrive*]. Thus, 459 participants will be enrolled to allow for this expected rate of attrition with the intent of capturing a range of evaluable data for 234 participants. The Power Analysis and Sample Size (PASS) 2015 software, version 14.02, was used to carry out the sample size and power analysis [18].

## **4. Human Subjects Protections**

### **4.1 Risks and anticipated benefits for trial participants**

Risk posed to participants will be minimal. Cognitive Behavioral Therapy modules are developed to provide supportive positive messages and examples for participants to work through. It is possible that participants will feel discomfort or stress in processing material and applying skills outside the program. Wait-list control group participants will receive standard National Institute of Mental Health information about depression while waiting 8 weeks for their access to *Thrive*.

### **4.2 Informing potential participants of possible benefit and known risks**

Study recruitment flyers and the informed consent forms notify potential participants of any possible benefits and risks. Participants are provided the contact information of the university's Institutional Review Board director and the study PI.

### **4.3 Obtaining informed consent from participants**

Potential participants will see the electronic informed consent, which details the information about study participation, on the study portal webpage. They must provide an electronic signature to confirm their understanding of study obligations.

### **4.4 Trial documentation**

Electronic data will be stored on secure encrypted servers and accessible only to the PI and study coordinator. Personal identifiable data are kept separate from health data. Paper records will be secured in locked file cabinets and offices. Data records will be retained for 7 years

upon study completion.

#### **4.5 Monitoring and reporting adverse events**

The PI will regularly monitor the data and indications of adverse events related to participation in the trial. If any adverse events are known to occur, the PI will promptly notify the university's Institutional Review Board to determine its relevance to the trial continuation. The *Thrive* program and the study assessment portal has prompts to help users who indicate suicidal ideation how to receive immediate help (see Appendix).

### **Messaging about the Appropriate Use of Thrive**

Before a study subject can start the Thrive curriculum, Thrive presents an “Important Information” page describing, in text written at the 5th grade reading level, the appropriate use of Thrive. The user cannot continue in Thrive without agreeing with the information on this page. See next page for a text of the Important Information page.

The main points on the Important Information page are:

- Thrive does not provide psychological advice, medical advice, diagnosis, or treatment
- The user may continue to see his/her doctor

*Below: an Important Information page is the first page a study subject sees after enrolling in Thrive. The subject cannot continue in Thrive without agreeing with this information.*

